4. TREATMENTS

4.1. STUDY TREATMENTS

4.1.1. Investigational Product and Apixaban Administration

Tissue Plasminogen Activator (tPA) is a commercially available drug approved for fibrinolysis of PE by systemic infusion at the dose of 100mg. tPA [Activase (alteplase)] (24mg) or placebo will be prepared by the research pharmacy.

Apixaban is an oral anti-Xa anticoagulant approved by the FDA for the treatment and prevention of venous thromboembolic disease. Study subjects will take 10mg by mouth twice a day for 7 days and 5mg by mouth twice a day thereafter for 12 months.

4.1.2.. HANDLING AND DISPENSING

Systemic (IV) tPA

Systemic (IV) tPA used in the study will be procured from the research pharmacy and prepared following pharmacy procedures and manufacturer instructions.

IV unfractionated heparin (Standard of Care)

Unfractionated heparin will be administered intravenously and is approved by the FDA for the treatment and prevention of venous thromboembolic disease. Unfractionated heparin will be procured from the main hospital pharmacy and prepared following pharmacy procedures and manufacturer instructions.

Apixaban anticoagulant

Apixaban will be provided by BMS for the duration of the study. It will be stored and dispensed by the research pharmacy. Atter completion of the study, the treating physician will determine if apixaban should be continued based on current guidelines and expert opinion. If the treating physician desires continuation of treatment, the subject will obtain this medication via usual channels.

4.2. METHOD OF ASSIGNING SUBJECT IDENTIFICATION

A subject who has signed informed consent and meets all eligibility criteria will be randomized by computer to receive either very low dose systemic (IV) tPA (24mg) + anticoagulation vs normal saline placebo (of same volume as systemic [IV] tPA) + anticoagulation. Subjects will be transitioned to apixaban 24 hours after study drug administration if subject has no evidence of active bleeding nor significant hemoglobin drop (i.e. \geq 2 mg/dL).

4.3. BLINDING AND UNBLINDING

All study personnel except the research pharmacy team will be blinded to intervention groups. The treatment medication and placebo will be prepared in similar IV bags and volumes. Assessments regarding clinical recovery will be conducted by an assessor blind to treatment allocation.

To maintain the overall quality and legitimacy of the clinical trial, unblinding should occur only in exceptional circumstances when knowledge of the actual treatment is absolutely essential for further management of the patient.

The Investigator is encouraged to maintain the blind as far as possible. The actual allocation must NOT be disclosed to the patient and/or other study personnel including other site personnel, monitors, BMS/Pfizer Alliance or project office staff; nor should there be any written or verbal disclosure of the code in any of the corresponding patient documents.

4.4. TREATMENT COMPLIANCE

The Investigator(s) or designee(s) is responsible for accounting for apixaban that is issued to and returned by the subject during the course of the study. Accurate recording of all apixaban administration (including dispensing and dosing) will be made in the appropriate section of the subject's CRF and source documents. Study personnel will review the instructions printed on the package with the study subjects prior to dispensing the study drug. The apixaban will be dispensed as noted in the Flowchart of Procedures. The subjects will be instructed to return the apixaban containers, including any unused apixaban, to the study site at each visit for tablet counts and reconciliation. Subjects will be asked whether they have taken their apixaban as instructed at each study visit. Any problems with apixaban compliance will be reviewed with the subject. If a subject misses 4 or more consecutive days of dosing, the investigator will decide whether dosing should resume or whether the subject should be terminated from the study drug and entered into the Posttreatment Observational Follow-up Phase.

Study drug compliance will be calculated at each visit as:X 100Compliance (%) = Number of tablets actually taken between visitsX 100Number of tablets that should have been taken between visitsX 100

4.5. DESTRUCTION OF STUDY DRUG

The research pharmacy will follow the CSMC drug destruction institutional policies.

5. STUDY ASSESSMENTS AND PROCEDURES

5.1. Screening Procedures

All subjects presenting for evaluation and treatment of intermediate-high risk PE will be considered for the study. All subjects that meet the study's inclusion criteria and do not meet any exclusion criteria are eligible for randomization into the study.

Potential subjects will be referred to the Pulmonary Embolism Response Team (PERT) by their treating physician. We will also identify potential patients through the Deep 6 AI Cohort Builder. Deep 6 will be the primary method of screening. If this primary method is not successful, then the study team is requesting a waiver of consent and HIPAA in order to conduct an additional secondary review of the patients' medical records. For the potential subjects identified via these methods, an investigator will discuss the study with their treating physician and seek permission to discuss the study with his/her patient. For patients referred by their treating physician or for patients who were identified by chart review and physician approval was granted, the informed consent process discussed in section 2.3 will be followed.

5.1.1. INFORMED CONSENT

The Cedars-Sinai Medical Center informed consent template will be used to create the SAFE-LYSE informed consent form. This template includes all elements required by ICH, GCP, and applicable regulatory requirements. The informed consent form will adhere to the ethical principles that have their origins in the Declaration of Helsinki. The consent will also include a statement that the Bristol-Myers Squibb Company will not continue to supply study drug to enrolled patients after conclusion of the

study. The study participant's treating physician will be responsible to ensure that they receive appropriate standard of care or other treatment for their condition.

The consent form, HIPAA Authorization and all recruitment materials will be approved by the Cedars-Sinai Medical Center Institutional Review Board (FWA 00000468). The informed consent form will be revised if new safety information becomes available or if there are any new additions to the protocol. Subjects currently enrolled in the study who may be affected by the new information will be reconsented.

5.2 ENROLLMENT

Subjects will be considered enrolled in the study at the time informed consent is obtained.

5.2.1. SCREENING ASSESSMENTS

The following assessments will be performed at Screening:

- Informed consent
- Medical history and demographics
- Inclusion/exclusion criteria
- Pregnancy test if the subject is female and of child-bearing potential.
- Vital signs and physical exam including blood pressure, respiratory rate, heart rate, and SpO2.
- Electrocardiogram (ECG; 12 lead)
- CT Angiogram to evaluate the anatomic location of PE (at least pulmonary or lobar artery involvement). The RV/LV ratio at end-diastole and the initial Refined Modified Miller obstruction index score will be determined from this image by a third party blinded radiologist.
- Echocardiogram to measure: RV dysfunction, RV/LV ratio, TAPSE, estimated RVSP, and collapse of the IVC with respiration.
- Laboratory testing including hemoglobin (Hgb), hematocrit (Hct), platelet count, blood urea nitrogen (BUN), creatinine, aPTT, PT and INR, liver function tests (ALP, ALT, AST), troponin I, and B-type natriuretic peptide and (BNP).
- Simplified Pulmonary Embolism Severity Index (sPESI) score calculation
- Lower extremity duplex ultrasound

5.3. RANDOMIZATION TO TREATMENT

A subject who has signed informed consent and meets all eligibility criteria will be randomized by computer to receive either very low dose systemic (IV) tPA (24mg) + anticoagulation vs normal saline placebo (of same volume as systemic [IV] tPA) + anticoagulation. Subjects will be transitioned to apixaban 24 hours after study drug administration if subjects have no evidence of active bleeding nor significant hemoglobin drop (i.e. $\geq 2 \text{ mg/dL}$).

All patients who give consent for participation and who fulfill the inclusion/exclusion criteria will be randomized. Randomization will be requested by the staff member responsible for recruitment from Randomize.net.

In return, Randomize.net will send an answer form to the research pharmacy, who are not involved in assessing outcome of the study. This form will include a randomization number. A closed envelope with printed randomization numbers on it are available on-site. For every randomization number, the corresponding code for the therapy group of the randomization list will be found inside the envelopes. The research pharmacy will open the envelope and will find the treatment condition to be conducted. Treatment medication will be prepped according to the randomization assignment. Staff responsible for recruitment and symptom ratings is not allowed to receive information about the group allocation.

5.3.1. SEQUENCE GENERATION

Subjects will be randomly assigned to either control or experimental group with a 1:1 allocation as per a computer generated randomization schedule using permuted blocks of random sizes. The block sizes will not be disclosed to ensure concealment.

5.3.2. CONCEALMENT MECHANISM

Subjects will be randomized using Randomize.net, which is an online, central randomization service. Allocation concealment will be ensured, as the service will not release the randomization code until the patient has been recruited into the trial, which takes place after all baseline measurements have been completed.

5.4. STUDY INTERVENTIONS

Eligible patients will be randomized in equal proportions between very low dose systemic (IV) tPA (24mg) + IV unfractionated heparin or saline placebo + IV unfractionated heparin. Study drug will be infused as follows: 4mg bolus IV push over 1 minute followed by 20mg infused IV over 19 minutes.

The study drug will be purchased from Genentech in its commercially available recombinant form. The study drug and placebo will be relabelled by the Cedars-Sinai Medical Center Research Pharmacy according to MHRA (Medicines and Healthcare Regulatory Agency) guidelines.

Study drug will be administered within 36 hours of anticoagulant administration. Study drug or placebo will be administered to the patient by a study-trained nurse while the patient is in hospital. All personnel will be blinded to the identity of the IV bag contents.

SAFE-LYSE Flowchart of Procedures											
Procedures	Baseline up to 48 hours pre study medication	Day 0	Day 1	Day 2	Day 3 & Day 7	Day 30 + 15 days (Clinic Visit)	Day 90 + 15 days (Phone contact)	Day 180 + 15 days (Clinic contact)	Day 270 + 15 days (Phone contact)	Day 365 + 15 days (Clinic Visit)	ET1
Informed consent	x										
Inclusion/Exclusion	x										
Randomization		x									
Heparin anticoagulation therapy ²	x	x	x								
Pregnancy test (if applicable)	x										
Medical and demographic history	x										
Physical exam	x		x			x		x		x	x
Vital signs including pulse ox	x	x	x	x		x		x		x	x

5.4.1. TREATMENTS AND TIMING

SAFE-LYSE Flowchart of Procedures											
Procedures	Baseline up to 48 hours pre study medication	Day 0	Day 1	Day 2	Day 3 & Day 7	Day 30 + 15 days (Clinic Visit)	Day 90 + 15 days (Phone contact)	Day 180 + 15 days (Clinic contact)	Day 270 + 15 days (Phone contact)	Day 365 + 15 days (Clinic Visit)	ET1
Chest contrast- enhanced computed tomographic angiogram (chest CTA)	x		x								
Echocardiogram	x		х			х		х			х
Ultrasound of lower expremities to rule out DVT	x										
ECG	х										
Hemoglobin, hematocrit, platelet count	х	х	х	х		х					
BUN, creatinine	х	x	-x			х					
Liver Function Tests	х		-			х					
aPTT, PT and INR	x	х	-								
Troponin I (or Troponin T)	х										
BNP	х										
sPESI	х		х								
Quality of life questionnaires						х		х		x	x
Administration of tPA/placebo		х									
Administration of apixaban ³			х	х	x	х		х			
6 Minute Walk and Borg Dyspnea scale						х		х		x	х
Remote health checks (phone and email)							х		х		
Review of medications and adverse events, bleeding events and VTE events	x	x	x	x	x ⁴	x	x	x	х	x	x

¹Early Termination: Obtain if subject withdraws early

²Heparin duration up to clinician discretion but patient must be on for at least 24 hours after infusion of study drug.

³Could start as early as soon as 24 hours post treatment, contingent upon clinician discretion.

⁴72-hour assessment of AE will be conducted either in person or if discharged via telephone call. Day 7 follow up will be telephone call.

Anticoagulation

All subjects will receive unfractionated IV heparin per standard of care with a goal of aPTT of 1.5 - 2 times control which is approximately 50-70 seconds, upon established diagnosis of PE.

Twenty-four hours after study drug administration, when the bleeding risk is determined to be low by the treating physician (i.e. no active bleeding nor significant hemoglobin drop $\geq 2 \text{ mg/dL}$), post-intervention evaluations are complete, the patient is tolerating oral medications, and the patient's creatinine clearance is >30 mL/min, the IV unfractionated heparin will be stopped. Provided bleeding risk is deemed acceptable, they will be immediately started on apixaban (Eliquis) 10 mg twice-daily x one week followed by 5 mg twice-daily for at least 6 months. Based on patient-specific factors, including unprovoked nature of PE event, and/or persisting DVT/PE risk factors, consideration will be given for decreasing the apixaban dose to 2.5 mg twice-daily after 6 months for the remainder of the study. The duration of total anticoagulation will be determined by the treating physician based on Clinic judgement, risk of recurrence, and whether the initial PE was provoked. Apixaban will be dispensed on Day 1, 30, and 180.

Timing of Thrombolytic Intervention

The subject will receive 24 mg of systemic (IV) tPA vs normal saline placebo within 24 hours of initiaition of anticoagulation therapy.

Systemic (IV) tPA

Commercially available formulation of systemic (IV) tPA (Genentech) may be used and all instructions for reconstitution provided in the package insert should be followed. tPA will be specially labeled for the study. The systemic (IV) tPA will be infused as follows: 4mg bolus followed by infusion at a rate of 20mg over 19 minutes for a total of 24mg.

Normal Saline Placebo

The pharmacy will prepare a normal saline placebo packaged in the same fashion as the systemic (IV) tPA. The saline will be infused as follows: 4mg bolus followed by infusion at a rate of 20mg over 19 minutes for a total of 24mg.

Day 0 Assessments: Pre-Infusion and Post-Infusion

- Vital signs including temperature, respiratory rate, heart rate, blood pressure, and oximetry will be obtained.
- Assessment of adverse events and bleeding events.

Day 1 Assessments

- Vital signs including temperature, respiratory rate, heart rate, blood pressure, and oximetry will be obtained.
- Physical Examination will be completed.
- Within 24 ± 8 hours of discontinuing treatment, the subject will be assessed for improvement in PE signs and symptoms including sPESI score, repeat CT angiogram for determination of thrombus burden as measured by a Refined Modified Miller Score and RV/LV ratio, and an echocardiogram.
- Laboratory tests for Hgb, Hct, platelet count, aPTT, PT and INR, BNP, troponin, BUN and creatinine will also be obtained.
- Adverse events, VTE recurrence, and bleeding events will be recorded.

Day 2 Assessments

- Vital signs including temperature, respiratory rate, heart rate, blood pressure, and oximetry will be obtained.
- Laboratory tests for Hgb, Hct, platelet count, aPTT, PT and INR, BUN and creatinine will also be obtained.
- Adverse events, VTE recurrence, and bleeding events will be recorded.

Follow-up Clinic Visits and Subject Contact

- The subjects will be followed until Day 365 ± 15 days.
- A 72-hour follow-up assessment of Adverse Events will be conducted either in-person if the subject is still admitted at CSMC, or via telephone call if the subject is discharged.
- A Day 7 follow-up assessment of Adverse Events will be conducted via telephone call.
- The subject will return to the clinic Day 30, 180 and 365.
- The following assessments will be performed at follow-up clinic visits:
 - Echocardiogram at Day 30 and Day 180. Echocardiogram will be repeated at Day 365/EOT if last echocardiogram was abnormal.
 - Blood draw for laboratory tests, including hemoglobin, hematocrit, platelet count, BUN, creatinine, and liver function tests at Day 30.
 Physical exam and vital signs including respiratory rate, heart rate, blood pressure, temperature, and sPO2
 - o 6MWT with Borg score and requirement for oxygen therapy
 - Quality of life (QOL) as measured by the PROMIS PF-6 and Pulmonary Embolism Quality of Life (PEmb-QOL)
 - Adverse Events through 1 year follow-up.
 - Signs or symptoms of recurrent VTE
 - Changes in anticoagulant medications
 - Evidence of chronic thromboembolic disease or chronic thromboembolic pulmonary hypertension
- Phone calls for remote health checks will be conducted at Day 7, Day 90 ± 15 days and Day 270 ± 15 days.

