	After delivery of the systemic (IV) tPA/placebo, patients will continue IV unfractionated heparin therapy for at least 24 hours. If there is no evidence of active bleeding nor significant hemoglobin drop (i.e., $\geq 2 \text{ mg/dL}$), patients will be transitioned to standard dose apixaban, 10 mg twice-daily x one week followed by 5 mg twice-daily for at least 6 months. Some patients will require indefinite apixaban therapy based on patient-specific factors, including unprovoked nature of PE event, and/or persisting DVT/PE risk factors. Finally, consideration will be given for decreasing the apixaban dose to 2.5 mg twice-daily after 6 months. Apixaban was selected as the anticoagulant of choice due to its very favorable bleeding profile in large clinical trials, which is an important consideration when prescribing an anticoagulant following systemic thrombolysis.
	Within 24 \pm 8 hours post study drug infusion, a repeat chest CTA and echocardiogram will be performed. sPESI will also be calculated at this timepoint.

٦

	At Day 30, 180 and 365, all subjects will have clinic visits which will include a physical exam, repeat echocardiogram (at Day 30 & 180), 6 minute walk test (6MWT), quality of life questionnaires, assessment of adverse and bleeding events and a review of concomitant medications including compliance with apixaban. At Day 3, 7, 90 and 270, a remote health check will occur via telephone or email assessing adverse and bleeding events, alongside a review of concomitant medications (including an assessment of compliance with apixaban).
	If any subject experiences an adverse event (AE), the investigator may, at his or her discretion, decrease or discontinue the study drug or apixaban.
	The DMC will meet after 10 subjects are enrolled; bleeding and other complications will be reviewed. An interim analysis will occur after 20 subjects have completed Day 30. The DMC will meet again after 30 subjects have completed Day 30. Because it is a single-center study, the investigators and study coordinators will be acutely aware of all adverse events.
	The primary analyses will compare the clot lysis on CTA in treatment A at 24 hours post study drug infusion. See Section 7 for a complete discussion of the statistical analysis.

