Inclusion Criteria	 Male or female 18-75 years in age Chest CT angiogram evidence of proximal PE with a filling defect in at least one main pulmonary artery or lobar artery PE symptom duration ≤14 days Intermediate-high risk PE: significant clot buden with RV dysfunction, an elevation in troponin > 0.05 ng/mL and/or brain natriuretic peptide (BNP) > 100 pg/mL, and hemodynamically stable (systolic blood pessure>90mm Hg without the use of vasopressor support) Randomization within 36 hours of anticoagulation Signed and dated informed consent obtained from subject or legally authorized representative before initiation of any study procedures
Exclusion Criteria	 Stroke or transient ischemic attack (TIA), head trauma, or other active intracranial or intraspinal disease within one year Recent (within one month) or active bleeding from a major organ Major surgery within 14 days Clinician deems the subject too high-risk for bleeding using HAS-BLED criteria. History of any hematologic disease or coagulopathy Cirrhosis (as determined by Child-Pugh B or C) History of heparin-induced thrombocytopenia (HIT) Hemodynamic instability defined as systolic blood pressure (SBP) less than 90 mm Hg and/or use of vasopressors for greater than 15 minutes Severe hypertension as define as systolic blood pressure (SBP) greater than 180 mm Hg Cardiac arrest or active cardiopulmonary resuscitation (CPR) Receiving neuraxial anesthesia or undergoing spinal puncture

Γ

	 Patient with prosthetic heart valves Evidence of irreversible neurological compromise Evidence of poor functional status History of major gastrointestinal bleed within the last month Active gastric or duodenal ulcers Use of thrombolytics or glycoprotein IIb/IIIa antagonists within 3 days prior to diagnosis Lovenox administration within 12 hours of randomization Direct-acting oral anticoagulant use (dabigatran, rivaroxaban, apixaban, or edoxaban) with last known dose within 48 hours Hemoglobin < 10 g/dL

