measured by RV/LV ratio. We also expect a very low risk of major bleeding, particularly when followed at 24 hours by apixaban which has been associated with a very low risk of major bleeding [24-25].

While even lower doses of systemic (IV) tPA have proven effective for acute PE when delivered by CDT [22], we are concerned that doses in the range of 8 to 12 mg, when delivered systemically, might be too low to confer benefit.

Patients with chest CTA-documented acute intermediate-high-risk PE (abnormal RV function by echocardiogram combined with an elevated troponin or BNP), who have no evidence of significant bleeding risk will receive systemic (IV) tPA (24 mg) combined with IV unfractionated heparin, or saline placebo and IV unfractionated heparin. After delivery of the systemic (IV) tPA, patients will continue IV unfractionated heparin therapy for 24 hours, and if the bleeding risk remains low, all patients will be subsequently transitioned to standard dose apixaban, 10 mg twice-daily x one week followed by 5 mg twice-daily at least 6 months (some patients will require indefinite apixaban therapy based on patient-specific factors, including unprovoked nature of PE event, and/or persisting DVT/PE risk factors). Finally, consideration will be given for decreasing the apixaban dose to 2.5 mg twice-daily after 6 monthslf bleeding suggests that a shorter acting anticoagulant (IV unfractionated heparin) should be continued longer, then it will be. Importantly, andexanet has now been FDA-approved for reversal of bleeding caused by apixaban, and will be available when our study is initiated [26]. After discharge, patients will be seen and followed in the Cedars-Sinai Pulmonary Embolism Response Team clinic.

We have specifically chosen to transition to apixaban based upon thevery low risk of major bleeding seen in large randomized clinical trials [24-25]. Finally, we will obtain long-term efficacy data including the effects of thrombolysis followed by apixaban on RV dysfunction, dyspnea and long-term mortality. Safety will be assessed by examining major and minor bleeding rates in all patients at 30 days, 60 days, and 6 and 12 months. Thus, will have data on apixaban in PE patients treated with thrombolysis.

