All imaging studies will be sent to the Syntactx core imaging laboratory for evaluation. Procedures for transfer of images from study site to Syntactx will be provided and we will maintain patient HIPAA confidentiality. Results of the assessments will be blinded and entered into the clinical database. All data from the study will be blinded and exclude information regarding the drug administered. Subjects will return for follow-up clinic evaluations at Day 30, 180 and 365 ± 15 days. It is anticipated that the clinical study duration will be up to 24 months including first subject enrolled through to last subject completed or until the study is formally terminated. An individual subject's participation will be approximately 1 year.

The figure below shows the schematic summary of the trial design:

* Provided bleeding risk is deemed acceptable, patients will be immediately started on apixaban 24 hours after study drug administration. The duration of total anticoagulation will be determined by the treating physician based on clinic judgement, risk of recurrence, and whether the initial PE was provoked.

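### The haemoglobin fall that blocks the switch from heparin to apixaban is printed in mg/dL in four places; the unit should be g/dL

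*Combined protocol and SAP*

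**What the plan says.** The rule for moving a patient from IV unfractionated heparin to apixaban is stated four times, each time with the same figure and unit:

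- Section 5.4.1, Anticoagulation, is the operative text. Heparin stops 24 hours after study drug if, among other conditions, the treating physician finds bleeding risk low, explained as "no active bleeding nor significant hemoglobin drop $\geq 2 \text{ mg/dL".
- Synopsis, Study Design and Methodology: "significant hemoglobin drop (i.e., $\geq 2 \text{ mg/dL}$), patients will be transitioned to standard dose apixaban".
- Section 4.2: "significant hemoglobin drop (i.e. \geq 2 mg/dL".
- Section 5.3: "significant hemoglobin drop (i.e. $\geq 2 \text{ mg/dL".

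The only other place where haemoglobin carries a unit is the exclusion criterion, in the synopsis and in Section 3.3.2: "Hemoglobin < 10 g/dL".

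Some wording leaves room for judgement. The note to the design figure in Section 3.2 reads "Provided bleeding risk is deemed acceptable, patients will be immediately started on apixaban 24 hours after study drug administration". Footnote 2 to the flowchart leaves heparin duration to the clinician after a 24-hour minimum, and footnote 3 makes the start of apixaban "contingent upon clinician discretion". Section 1.1 allows heparin to run on: if "bleeding suggests that a shorter acting anticoagulant (IV unfractionated heparin) should be continued longer, then it will be".

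**The concern.** The figure is a decision threshold in a bleeding-safety rule that applies shortly after thrombolysis. Haemoglobin is measured at baseline and on Days 0, 1 and 2, so real laboratory values will be set against it. As printed, the threshold is so small that almost any recorded fall would count as significant and would hold the patient on heparin. Staff would then have to choose between the printed rule and the one presumably intended. Following the intended rule would, on paper, depart from the protocol, and Section 9.1.1 does not allow a deviation without IRB approval except to remove immediate danger.

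**Working it through.** No derived figure in the plan has to be reproduced here. The check is a unit conversion and a comparison with the protocol's own haemoglobin unit.

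**Inputs**

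- Threshold as printed: a fall of 2 mg/dL or more (synopsis; Sections 4.2, 5.3 and 5.4.1).
- Lowest eligible haemoglobin: 10 g/dL (synopsis exclusion criteria; Section 3.3.2).
- Conversion: 1 g = 1,000 mg.

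**Printed threshold in the protocol's unit**

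2 mg/dL ÷ 1,000 = 0.002 g/dL.

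**Relative to the eligibility floor**

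10 g/dL = 10,000 mg/dL.

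| Threshold | In mg/dL | Share of 10,000 mg/dL |
|---|---|---|
| As printed, 2 mg/dL | 2 | 2 / 10,000 = 1/5,000 = 0.02% |
| With g/dL, 2 g/dL | 2,000 | 2,000 / 10,000 = 1/5 = 20% |

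Ratio of the two: 2,000 / 2 = 1,000.

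**What the printed rule would catch**

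The smallest fall a laboratory can record is one reporting step. If the step is 0.002 g/dL or coarser, every recorded fall meets the printed threshold. The documents do not give the step. Assuming a range of 0.01 to 0.1 g/dL:

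- 0.01 g/dL = 10 mg/dL, and 10 / 2 = 5 times the threshold.
- 0.1 g/dL = 100 mg/dL, and 100 / 2 = 50 times the threshold.

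**Could it be an artefact of text extraction?** This is unlikely. The unit reads mg/dL in all four places, one of them (Section 4.2) as plain text, while the exclusion criterion comes through correctly as g/dL in both of its places.

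**Does other text correct it?** No. Nowhere is the fall given in g/dL. Section 3.5 interrupts apixaban for a significant fall but gives no number, and its later mention of a haemoglobin below 10 has no unit, though it makes sense only in g/dL.

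**The case against.** The strongest reply is that this is one slip copied four times and that it reveals itself. No calculation fails. A physician, not a program, applies the rule, and would almost certainly read it as 2 g/dL. The next sentence of Section 5.4.1, the note in Section 3.2 and flowchart footnotes 2 and 3 all add clinical judgement with no number attached. If the rule were applied literally, the error would only keep a patient on heparin longer. It could not bring apixaban forward.

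Most of this stands, and it is why the point is minor. It does not remove the error. Section 5.4.1 defines the physician's low-risk judgement by this figure, and the synopsis and Sections 4.2 and 5.3 state the condition in sentences that mention no discretion. That readers would probably ignore the printed unit is a reason to correct it.

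**Conclusion.** The unit is wrong as written, by a factor of 1,000. That g/dL was meant is an inference from the exclusion criterion's unit and from the word significant, but no other reading is plausible. The statement that essentially any recorded fall would hold the switch rests on a laboratory step of 0.002 g/dL or coarser, which the documents do not give. The documents also do not support an estimate of how many patients would be affected, and none is made.

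The consequence is limited. The rule is the same in both blinded arms. Section 5.4.1 also requires the post-intervention evaluations to be finished before heparin stops, and the repeat CTA is among the Day 1 evaluations, so under that section the switch should follow the primary measurement; the other three statements do not carry this condition. Sample size, power, the primary analysis and the GUSTO bleeding definition do not depend on the figure. Severity: minor.

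**What to change.** Replace mg/dL with g/dL in the synopsis (Study Design and Methodology) and in Sections 4.2, 5.3 and 5.4.1, so that the threshold is a fall of 2 g/dL or more, and have the clinical team confirm that value. Nothing else has to change for this correction. The cost is a wording amendment in four places, with no added patients, procedures or analyses and no new clinical rule.
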